The ZX008 0.8 mg/kg/day group will be compared to the placebo group on the percent change from baseline in seizures resulting in drops using a Wilcoxon rank-sum test. The median difference between the groups, and its 95% confidence interval, will be estimated using the Hodges-Lehmann estimator.

Impact of Antiepileptic Drugs (AED)

Subjects in the study are required to be on stable background therapy. Using the MITT population, an additional nonparametric ANCOVA analysis will be performed to assess the impact on the primary analysis of changes in dose or type of concomitant AED, which are protocol violations that may occur during the course of the study.

For this analysis, each subject will be classified according to the number of concomitant AEDs used during the T+M period. Fisher's exact tests will be used to compare the

active dose groups with the placebo group on the percentage of subjects within each group who have a change in concomitant AEDs.

Per protocol Analysis

The primary efficacy ANCOVA will be repeated on the per protocol population (which excludes subjects with important protocol deviations that may affect the inference on efficacy such as a change in dose or type of concomitant AED).

No Imputation for Seizure Clusters

The primary efficacy ANCOVA will be repeated on the mITT population with no imputation for seizure clusters; i.e., seizure clusters will not be calculated in the frequency of seizures that result in drops.

Exclusion of Outliers

The distribution of the primary endpoint is inherently asymmetric since no subject can have more than a 100% decrease in seizures, but there is no reason a subject couldn't have a 200% or even 1000% increase. In fact, there is no theoretical upper bound to the possible magnitude of an increase in a percent change statistic. To assess the sensitivity of the primary analysis to extreme outliers in percent change in drop seizure frequency, the primary analysis will be repeated excluding any PCDSF value that satisfies Tukey's criterion for a "far out" outlier (Tukey, 1977). Specifically, any PCDSF value that satisfies

$$[\hat{q}_{.25} - 3(\hat{q}_{.75} - \hat{q}_{.25}), \qquad \hat{q}_{.75} + 3(\hat{q}_{.75} - \hat{q}_{.25})]$$

will be excluded where $\hat{q}_{.25}$ and $\hat{q}_{.75}$ are the sample lower and upper quartiles of the all PCDSF data combined.

Imputation for Dropouts

Two different methods for imputation of missing values due to subject drop out will be incorporated into the analysis of the primary efficacy endpoint. When referring to frequency in the paragraphs below, it refers to the number of seizure events per 28 days.

S1: Worst value substituted: In this analysis, for a subject who drops out of treatment, if the drop seizure frequency during T+M is lower than the baseline value, the baseline value will be substituted for the subject from the point of withdrawal to the end of the planned duration of T+M. However, if the seizure frequency during T+M is higher than the baseline value, there will be no substitution. The DSF for the planned duration of T+M will then be computed as a weighted mean of the value before dropout, and the imputed value after dropout. The weights will be the proportion of planned duration of T+M before and after dropout. The statistical analysis (nonparametric ANCOVA) described at the start of section 8.2.2 will then be performed on the resulting dataset. Treatment comparisons will be based on the least squares means and standard errors obtained from the ANCOVA.

S2: Differential imputation method: In this analysis, subjects who dropout due to an adverse event, lack of compliance, loss to follow-up or subject choice will have their

convulsive seizure frequency for the remainder of the time during the planned T+M period replaced with the worse of the observed value or the baseline value as described for S1. However, for other withdrawal reasons (e.g., "lack of efficacy") their observed DSF during T+M will be imputed for the remainder of the time between dropout and end of planned T+M. The DSF for the planned duration of T+M will then be computed as a weighted mean of the value before dropout and the imputed value after dropout. The weights will be the proportion of time before and after dropout. The statistical analysis (nonparametric ANCOVA) described at the start of section 8.2.2 will then be performed on the resulting dataset. Treatment comparisons will be based on the least squares means and standard errors obtained from the ANCOVA.

Criteria for Establishing Efficacy

While several supportive and/or supplementary analyses are specified above, the main criterion for demonstrating efficacy will be the primary non-parametric analysis for the mITT population from Cohort A.

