6.7. VISIT WINDOWS

The following rules will be used to window data into treatment periods for by treatment period tabulations. For all by-visit tabulations, the nominal visit as recorded on the electronic Case Report Form (eCRF) will be used.

The following are the definitions for associating dates with the treatment periods of Part 1.

Baseline Period	The Baseline Treatment period will be the 28 days immediately prior to the date of the Study Day 1.
Double Blind	The Double-Blind Treatment Period start date is the date of
Treatment Period	first full daily dose (i.e. Study Day 1). The Double-Blind
Sell Call	Treatment Period end date is the last date the subject was on study treatment in Part 1.
Chy, Oblig	The Double-Blind Treatment Period consists of 16 weeks from first treatment start date, which includes 2 weeks of
S. S.	Titration period, 12 weeks of Maintenance period and 2 weeks of Taper/Transition period. The end date for efficacy
	analyses is the last day of Maintenance treatment, or Visit 12; the end date for safety analyses is the last day of

version 2.0	Syneos Health #1009529	7A
	Taper/Transition, which would be considered the date at Visit 15.	ation
	For subjects who discontinue early from the study, the double-blind treatment period end date for efficacy analyses will be the date at the early termination visit (Visit 12); the end date for safety analyses would be the date of Visit 13. If a taper is not conducted, the end date for both analyses would be Visit 12.	alithorization ereof.
Titration Period	The Titration Period begins on the first full day of treatment (Study Day 1) and extends through Visit 6 (when the subject has reached their randomization dose). The Titration Period applies to all subjects including placebo recipients. If a subject withdraws from the study prior to treatment in the maintenance period, all safety assessments and events up to and including the date of study withdrawal will be tabulated in the titration period.	ere .
Maintenance Period	The Maintenance Period covers the 12 weeks following the end of the titration period. It begins on the date of Visit 6 + 1 day and extends through the end of study/early termination visit (Visit 12).	
Titration + Maintenance Period (T+M)	The T+M period combines the Titration and Maintenance periods, beginning on the date of first treatment (Study Day 1) and extending through the end of study/end of treatment visit (Visit 12).	

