6.9. SUBGROUPS

The following subgroups will be utilized for some efficacy analyses and adverse event summarizations:

Version 2.0

Syneos Health #1009529A

Age: 2- <6 years, 6-<12 years, 12 - <18, 2-<18 years, \geq 18 - 35 years.

Sex: Male, Female

Baseline Weight: <37.5 kg vs. ≥ 37.5 kg

Number of concomitant Antiepileptic Medications Used: ≤ 2 , 3, ≥ 4 medications

Number of prior Antiepileptic Medications Used: 0-3, 4-6, 7-9, ≥10 medications

Baseline Frequency of Seizures that Result in Drops (events/28 days): based on observed tertiles

Usage of a specific concomitant medication(s) (top 3 concomitant AEDs to be determined by data review) (Yes / No)

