Figure	14.2.1.5.1.1	Cumulative Response Curve for Percent of Subjects Experiencing Various % Reductions in Seizures Resulting in Drops (ESC Confirmed) during Part 1 (Cohort A - North America, Europe, Australia) - mITT Population	
Figure	14.2.1.5.1.2	Cumulative Response Curve for Percent of Subjects Experiencing Various % Reductions in Seizures Resulting in Drops (ESC Confirmed) during Part 1 (Cohort B - Japan) - mITT Population	
Table	14.2.1.6.1	Frequency of Seizures Resulting in Drops (ESC Confirmed) per 28 days during Part 1 by Age Subgroup: Nonparametric Analysis (Cohort A - North America, Europe, Australia) - mITT Population	
Table	14.2.1.6.2	Frequency of Seizures Resulting in Drops (ESC Confirmed) per 28 days during Part 1 by Sex: Nonparametric Analysis - (Cohort A - North America, Europe, Australia) mITT Population	
Table	14.2.1.6.3	Frequency of Seizures Resulting in Drops (ESC Confirmed) per 28 days during Part 1 by Weight Subgroup: Nonparametric Analysis - (Cohort A - North America, Europe, Australia) mITT Population	
Table	14.2.1.6.4	Frequency of Seizures Resulting in Drops (ESC Confirmed) per 28 days during Part 1 by Number of Concomitant Antiepileptic Medications Used:	

Versi	on 2.0	Syneos Health #1009529A	
		Nonparametric Analysis (Cohort A - North America, Europe, Australia) mITT Population	rilation.
Table	14.2.1.6.5	Frequency of Seizures Resulting in Drops (ESC Confirmed) per 28 days during Part 1 by Number of Prior Antiepileptic Medications Used: Nonparametric Analysis (Cohort A - North America, Europe, Australia) mITT Population	notilati
Table	14.2.1.6.6	Frequency of Seizures Resulting in Drops (ESC Confirmed) per 28 days during Part 1 by Baseline Frequency of Seizures that Result in Drops: Nonparametric Analysis (Cohort A - North America, Europe, Australia) - mITT Population	eo'i.
Table	14.2.1.7.1	Frequency of Seizures Resulting in Drops (ESC Confirmed) per 28 days during Part 1: Nonparametric Analysis - Sensitivity to Missing Data Analysis 1 (Worst Value Substituted for Dropouts) (Cohort A North America, Europe, Australia) - mITT Population	
Table	14.2.1.7.2	Frequency of Seizures Resulting in Drops (ESC Confirmed) per 28 days during Part 1: Nonparametric Analysis - Sensitivity to Missing Data Analysis 1 (Worst Value Substituted for Dropouts) (Cohort B - Japan) - mITT Population	

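### The AED sensitivity ANCOVA in Section 8.2.3 is meant to test changes in background AEDs but classifies subjects by how many AEDs they used

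*SAP*

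**What the plan says.** Section 8.2.3, under the heading on the impact of AEDs, notes that background therapy should be stable. It then adds a nonparametric ANCOVA on the mITT population "to assess the impact on the primary analysis of changes in dose or type of concomitant AED", and describes such changes as ones "which are protocol violations that may occur during the course of the study". The method follows directly: "each subject will be classified according to the number of concomitant AEDs used during the T+M period". The text does not say how that class enters the model (factor, interaction, stratum or exclusion).

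The same paragraph adds Fisher's exact tests comparing the "active dose groups with the placebo group on the percentage of subjects within each group who have a change in concomitant AEDs". The next analysis in Section 8.2.3 is the per-protocol ANCOVA, which leaves out subjects with important deviations, "such as a change in dose or type of concomitant AED".

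Section 6.9 already lists "Number of concomitant Antiepileptic Medications Used" as a subgroup, in classes of at most 2, 3, and 4 or more. Section 14 lists the matching nonparametric output as Table 14.2.1.6.4.

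**The concern.** The question is about change and the classifier is about quantity. A subject can have any number of AEDs with no change, and can have a change without the number moving. An ANCOVA that sorts subjects by number therefore says whether the treatment effect differs between people on few and on many drugs. It does not say what AED changes did to the primary comparison.

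At stake is a robustness check that the plan promises and does not deliver. A reader of the study report could take the by-number result as reassurance that AED changes did not matter, when the analysis could not have shown it either way. T+M begins on Study Day 1 (Section 6.7), so the count is also taken after randomisation and on treatment.

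**Working it through.** The plan states no figure on this point, so the check is of the wording, with one small illustration.

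**Step 1. Does the count register a change?** Section 8.2.3 gives no classes, so I assume those of Section 6.9.

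| Subject during T+M | AED count | Class | Change? |
|---|---|---|---|
| A: two AEDs, stable | 2 | at most 2 | no |
| B: two AEDs, one dose changed | 2 | at most 2 | yes |
| C: two AEDs, a third added | 3 | 3 | yes |
| D: three AEDs, stable | 3 | 3 | no |
| E: three AEDs, one swapped | 3 or 4 | 3, or 4 or more | yes |
| F: four AEDs, stable | 4 | 4 or more | no |

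A and B share a class although only B changed, and so do C and D although only C changed. A and F are split although neither changed. E depends on a point that Section 8.2.3 leaves open. If every drug used in the period is counted, as the definition of concomitant medication in Section 7.4 would suggest, a one-for-one swap adds one. If drugs taken at the same time are counted, it adds none.

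**Step 2. How many changers would even move class?** Let d be the share of changes that are dose-only, and suppose every other change adds one drug to the count. A changer then moves class only if the starting count is 2 or 3:

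share moving class = (1 − d) × P(starting count is 2 or 3)

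The SAP gives no distribution of AED counts. Assume probabilities 0.10, 0.25, 0.35, 0.20 and 0.10 for 1 to 5 drugs. Then P = 0.25 + 0.35 = 0.60, and:

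| d | Share of changers who move class |
|---|---|
| 1.0 | 0 × 0.60 = 0% |
| 0.8 | 0.2 × 0.60 = 12% |
| 0.5 | 0.5 × 0.60 = 30% |
| 0 | 1 × 0.60 = 60% |

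The first row holds whatever the distribution. In the others, a subject who moves class still cannot be told apart from a stable subject already there, as C and D show.

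**Step 3. Does the output list repair it?** In Section 14 the nonparametric sensitivity outputs for the primary endpoint cover dropouts (14.2.1.7), the Wilcoxon test (14.2.1.8), outliers (14.2.1.9) and clusters (14.2.1.10). The only AED-number output is 14.2.1.6.4, which is the Section 6.9 subgroup. No efficacy output is titled by AED change. The SAP addendum keeps 14.2.1.6.4, adds a version of it on the updated drop-seizure file, and adds nothing by AED change.

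**Step 4. Do the neighbouring analyses answer the question?** The Fisher tests compare the frequency of changes between arms and carry no seizure outcome. The per-protocol ANCOVA carries the outcome. However, Section 6.4 also excludes subjects with other major deviations, those with under 4 weeks of maintenance diary data, and those not meeting the baseline drop-seizure criterion. A difference from the mITT result cannot be assigned to AED changes, and changers' data from before the change are lost.

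**The case against.** The best defence is that the plan is not blind to AED changes. The Fisher tests would show an imbalance in how often they occur. The per-protocol ANCOVA excludes changers, and its exclusions are fixed before unblinding. Both points stand, and they make this a gap in one supportive analysis, not a general failure to examine AED changes. They do not rescue the ANCOVA, whose stated question is the impact on the primary result.

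Some stronger inferences are tempting and not supported:

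- A reader might infer that the primary estimate is confounded. AED changes after randomisation are not confounders of a comparison analysed as randomised; they affect how the estimate is interpreted. If more AED lowers seizure frequency, increases on placebo or reductions on active drug would shrink the ZX008 advantage. Only the reverse pattern would inflate it, and the SAP gives neither a rate nor a direction.
- A reader might reach for the S1 dropout rule, which substitutes the baseline value after the event when the observed value is lower. Where AED increases were commoner on placebo, that would erase placebo improvement and could favour active drug, so it is a poor default here.
- A reader might assume that all the dates needed are on file. The addendum confirms start and stop dates on the Concomitant Medications eCRF page; it does not say how a dose change is dated.

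**Conclusion.** The point holds in this form: the classifier does not match the stated purpose, so the AED sensitivity ANCOVA as written cannot show the impact of AED changes on the primary result, and it largely duplicates an existing subgroup table. That the count misses dose changes follows from the wording and needs no assumption. The class-movement percentages for other changes rest on the assumed distribution of AED counts, the Section 6.9 classes and the rule that each such change adds one drug.

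No effect on the treatment estimate can be given, because the SAP states no frequency of AED changes. Section 8.2.3 makes the primary nonparametric mITT analysis in Cohort A the main efficacy criterion, and that is unaffected. The point is worth correcting, but no efficacy decision depends on it.

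**What to change.** In the AED paragraph of Section 8.2.3:

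1. Replace the count by an indicator of any change in dose or type of concomitant AED during T+M (yes/no), with the date of first change where recorded.
2. Repeat the primary rank ANCOVA of Section 8.2.2 on the mITT population, computing each subject's T+M drop-seizure frequency from diary data only up to the first AED change. If dose-change dates are not available, exclude only the subjects with a change.
3. State what is done with a subject whose change leaves less than the one week of diary data that mITT membership requires.
4. Keep the Fisher tests on the same indicator, and add the output to the index. The by-number analysis stays as the Section 6.9 subgroup.

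The cost is some SAP wording and one more run of an existing model, after confirming how dose changes are recorded. The indicator is itself a post-randomisation event, so the analysis remains supportive. Cutting the diary at an early change also leaves a short, titration-heavy record for that subject. The addendum describes Cohort A Part 1 analyses as completed, so for Cohort A the result would have to be labelled post hoc.

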8.2.4. Key Secondary Analysis of the Primary Efficacy Endpoint

The first key secondary endpoint compares treatment groups on the percentage of subjects with at least a 50% reduction from baseline in seizures resulting in drops. That is, the proportion of subjects in the ZX008 0.8 mg/kg/day group who have a decrease in frequency of seizures resulting in drops of at least 50 percentage points will be compared to the analogous proportion in the placebo group. This the 1st key secondary efficacy endpoint.

The comparison of the percentage of subjects with at least a 50 percent drop from baseline between treatment groups will be made using a logistic regression model that incorporates the factors treatment and weight strata and the baseline seizure frequency. Separate models will be fit for ZX008 0.2 mg/kg/day vs. placebo and ZX008 0.8 mg/kg/day vs. placebo. Achievement of the 50 percentage point reduction or greater, yes or no) will be modeled as a function of treatment group (2 levels; ZX008 0.8 mg/kg/day (or ZX008 0.2 mg/kg/day) and placebo) and baseline weight strata group (<37.5 kg, \geq 37.5 kg). If the model with treatment and weight strata is not convergent (e.g. due to a 0 count in a treatment by weight strata combination, the model will be refit using treatment only and the baseline seizure frequency. If the model still does not converge, no odds ratio and p-value from the logistic regression will be reported.

The model estimated odds ratio (including a 95% confidence interval) and p-value for comparison of ZX008 0.8 mg/kg/day to placebo and ZX008 0.2 mg/kg/day to placebo will be provided. A supplementary Fisher's exact test comparing treatment groups will be provided.

Similarly, the number and percentage of subjects who have a worsening, $\ge 0\%$ reduction, $\ge 25\%$ reduction, $\ge 50\%$ reduction, $\ge 75\%$ reduction, $\ge 100\%$ reduction, and near seizure-freedom will be tabulated for each treatment. Near seizure-freedom will be defined as having 0 or 1 seizures leading to a drop in the T+M period. These are additional secondary endpoints.

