Part 1 consists of a 4-week baseline, 2-week titration, 12-week maintenance, and 2week taper or transition period. The 4-week Baseline Period consists of the establishment of initial eligibility during a screening visit to include an assessment of cardiac parameters (ECG and ECHO), followed by an observation period where subjects will be assessed for baseline seizure frequency based on recordings of daily seizure activity entered into a diary. Upon completion of the Baseline Period, subjects who qualify for the study are randomized (1:1:1) in a double-blind manner to receive 1 of 2 doses of ZX008 (0.2 mg/kg/day, 0.8 mg/kg/day; maximum dose: 30 mg/day [or 0.5] mg/kg/day, maximum 20 mg/day, for subjects taking concomitant STP]) or placebo. Randomization is stratified by weight (<37.5 kg, $\ge 37.5 \text{ kg}$) to ensure balance across treatment arms, and at least 25% of subjects will be in each weight group. All subjects are titrated to their blinded randomized dose over a 2-week Titration Period. Following titration, subjects continue treatment at their randomly assigned dose over a 12-week Maintenance Period. Total treatment time from the beginning of the Titration Period through the end of the Maintenance Period is 14 weeks. Subjects will have ECG and ECHO assessments at weeks 6 and 14 during the Maintenance Period. At the end of the Maintenance Period (or early discontinuation), all subjects undergo a blinded 2-week taper or transition period (Post-Dosing Follow-Up) depending on whether they exit the study or are enrolled in Part 2, the long-term open-label extension, respectively. Cardiac safety follow-up visits are performed after study drug discontinuation for early termination, or for those subjects who complete the study but do not enter the openlabel extension part. All subjects are required to have follow-ups at 3 and 6 months. Subjects enrolled in Germany, France and Netherlands will have an additional follow-up at 24 months. If there are any findings at a post-dose follow-up, a follow-up visit will be scheduled every 3 months until resolved or stabilized.

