4.2. DETERMINATION OF SAMPLE SIZE

The sample size for Part 1 Cohort A was estimated under the assumption that adding ZX008 at 0.8 mg/kg/day to current therapy will lead to a mean decrease in drop seizures that is 30 percentage points greater than adding placebo to current therapy. For example, if adding placebo leads to a 10% decrease in seizures, then adding the high dose of ZX008 would be expected to decrease seizures by at least 40%. The variability expected in the trial was estimated from a Phase 3 trial of clobazam for patients with Lennox-Gastaut syndrome (Ng 2011) leading to an assumption that the standard deviation (SD) is 50%. Other assumptions include an allowance for 20% dropouts between randomization and the start of the maintenance period. Under these assumptions, a sample size of 63 subjects per treatment group for a nonparametric analysis affords 90% power to detect a difference between the ZX008 0.8 mg/kg/day and placebo groups that is significant at the α =0.05 level. Assuming a 20% drop-out rate prior to the start of the maintenance period yields a requirement for an additional 14 subjects per group for a total of 79 subjects per treatment group for a nonparametric analysis. Similar calculations for the 0.2 mg/kg/day ZX008 group lead to a total required

sample size of 237. The number of subjects randomized into Part 1 Cohort A is estimated to be approximately 250 due to the long baseline period.

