6.3. MODIFIED INTENT-TO-TREAT (MITT) POPULATION

Salthoril Ation The mITT Population is defined as all randomized subjects who receive at least one dose of ZX008 or placebo and for whom at least one week of diary data are available. Subjects will be analyzed according to the treatment group to which they were randomized. The primary comparison of ZX008 0.8 mg/kg/day to placebo, as well as key secondary analyses, will be performed on the mITT Population.

PER PROTOCOL (PP) POPULATION 6.4.

The PP Population is defined as all randomized subjects who receive at least one dose of ZX008 or placebo, who complete at least 4 weeks of diary data in the maintenance period, and who have no major protocol deviations that would have a significant impact on clinical outcome of Part 1 data, and who have met the inclusion criteria for baseline drop seizure count. Protocol deviations that occurred during Part 1 will be reviewed and the list of deviations warranting exclusion from the PP Population will be finalized prior to study unblinding.

PROTOCOL DEVIATIONS 6.5.

Major protocol deviations will be summarized overall and by site based on the SAF population. Major protocol deviations are those that have the potential to impact subject safety and/or affect data integrity and/or the efficacy conclusions. Major protocol deviations will be grouped into categories and may include categories such as:

- Violation of inclusion/exclusion criteria
- Violation of randomization inclusion criteria
- Non-compliance regarding intake of IMP
- Inappropriate intake of concomitant medication
- Subject not discontinued as per protocol
- Other non-compliance

Multiple deviations can occur in the same subject and thus a subject can be counted in more than 1 deviation category.

Major and minor protocol deviations will be presented in a subject data listing for the enrolled population, sorted by treatment, site, subject, and study part.

Deviations will be reviewed prior to the database lock of Part 1 data to determine which deviations will be classified as leading to exclusion from the PP set.

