8.2. PRIMARY EFFICACY ENDPOINT AND ANALYSIS

8.2.1. Primary Efficacy Endpoint Definition

The Part 1 primary efficacy endpoint is the percent change from baseline in the frequency in seizures that result in drops per 28 days in the T+M period. The following seizure types from the DSD will be included in the frequency count of seizures resulting in drops, if for an individual subject, the seizure as listed in the eCRF has been confirmed and approved by the Epilepsy Study Consortium (ESC) as a 'drop seizure':

- atonic seizures [AS]
- tonic seizures [TS]
- tonic/atonic seizures [TA]
- generalized tonic-clonic seizures [GTC]
- secondarily generalized tonic-clonic [SGTC]

For each subject, the frequency of drop seizures will be calculated from all available data collected during the Baseline and T+M Periods. Subjects in the ZX008 0.8 mg/kg/day treatment group will be compared to those in the placebo on the frequency of drop seizures (DSF) during T+M adjusted for the frequency during Baseline using a non-parametric ANCOVA model.

The baseline period is the 28 days immediately preceding the date of Study Day 1. The T+M period is planned for 14 weeks. However, actual durations will be computed for

each subject based on the individual subject's start and stop dates for each period, except that if the baseline period is longer than 28 days, the frequency for the baseline period will be calculated with data from the 28 days immediately preceding the Study Day 1.

The frequency of drop seizures will be counted from the daily diary records provided by the Subject or Parent/Caregiver.

Responses to the DSD question about the frequency of seizure episodes will be handled differently according to the following response options.

Response	Number of seizures
No seizures	0
A single seizure	1
An episode of many discrete seizures	Based on the response to the Question 12 for frequency of episodes
A cluster of seizures back to back	This will be determined empirically dependent on the duration of the cluster event and the number of events reported in a discrete seizure event for subjects in the study.

Seizure Clusters

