Seizure clusters are entered in the DSD by estimating the duration of the cluster in hours: minutes; seconds. For seizure clusters the number of discrete seizures that occurred during a cluster is not entered in the DSD. In order to estimate the number of seizures during a cluster, the number of seizures will be imputed using the seizure count and duration of seizures recorded for "an episode of many discrete seizures".

Specifically, episodes of discrete seizures include both an estimate of the number of seizures, and an estimate of the duration, categorized into 1 of 3 buckets: <2 minutes; 2-10 minutes; >10 minutes.

Study-level summary statistics using seizure events reported in the T+M period will be calculated for each bucket to determine the median number of seizures occurring in each bucket.

The median number of seizures will then be used to impute counts for seizure clusters:

- 'short' clusters (i.e., ≤59 minutes) will be the median number of seizures reported in discrete seizure events <2 minutes
- 'medium' clusters (i.e., 1-5 hours) will be the median number of seizures reported in discrete seizure events 2-10 minutes

• 'long' clusters (i.e., >5 hours) will be the median number of seizures reported in discrete seizure events >10 minutes.

For any individual subject, the frequency of drop seizures per 28 days during the baseline period (DSF_B) will be derived as follows:

$$DSF_B = \frac{28 \times Total\ number\ of\ drop\ seizures\ during\ the\ Baseline\ Period}{Total\ number\ of\ days\ in\ the\ Baseline\ Period\ with\ nonmissing\ diary\ data}$$

For each treatment group, the median and mean DSF_B will be calculated.

Similarly, for each subject, the frequency of DSF per 28 days for the T+M period (DSF $_{T+M}$ is derived as below:

$$DSF_{T+M} = \frac{28 \times Total \text{ number of drop seizures during the } T + M \text{ Period}}{Total \text{ number of days in the } T + M \text{ Period with nonmissing diary data}}$$

The percentage change from baseline for any individual subject will be estimated by $PCDSF_{T+M} = (DSF_{T+M} - DSF_B)*100/DSF_B$

The difference from baseline (CDSF_{T+M}) will be estimated by CDSF_{T+M} = DSF_{T+M} – DSF_B.

For each treatment group, descriptive statistics for DSF during baseline, T+M and M only, as well as the differences and % changes from baseline, will include the number of observations, mean, standard deviation, median, minimum and maximum, overall.

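### Near seizure-freedom and 100% reduction have no rule for early leavers, so a subject with one week of diary can meet them by chance

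*SAP*

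**What the plan says.** Section 8.2.4 of the SAP sets the rule: "Near seizure-freedom will be defined as having 0 or 1 seizures leading to a drop in the T+M period". It tabulates this category next to graded percentage reductions up to 100% and classes them all as additional secondary endpoints.

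Three other sections fix how much observation lies behind the count:

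- Section 4 gives the planned length: "Total treatment time from the beginning of the Titration Period through the end of the Maintenance Period is 14 weeks".
- Section 6.7 closes the efficacy period of an early leaver at the early termination visit.
- Section 6.3 admits to mITT any dosed, randomized subject "for whom at least one week of diary data are available".

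The percentage categories are built differently. Under Section 8.2.1, "the frequency of drop seizures will be calculated from all available data collected during the Baseline and T+M Periods", as drop seizures per 28 days of non-missing diary (DSF). Percent change is taken between the two rates. The ≥50% responder endpoint in Section 8.2.4 counts subjects "who have a decrease in frequency of seizures resulting in drops of at least 50 percentage points", so it also rests on a rate. It is steps 2 and 5 of the hierarchy in Section 8.1. Near seizure-freedom and 100% reduction are in none of the six steps.

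The dropout imputations S1 and S2 (Section 8.2.3) apply to the primary endpoint and its rank ANCOVA. Section 8 repeats the key secondary analyses in the PP population, which requires at least four weeks of Maintenance diary (Section 6.4).

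**The concern.** A fixed ceiling of one seizure is easier to stay under for one week than for fourteen. As written, leaving early raises the chance of being scored near seizure-free, whatever the drug does. A 100% reduction behaves the same way, because a zero rate means only that no seizure was recorded in the days observed.

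Early leaving is planned for. Section 4.2 says: "Other assumptions include an allowance for 20% dropouts between randomization and the start of the maintenance period". If one arm loses more subjects during titration, it can collect more apparent successes in the two categories that readers take as the strongest clinical result.

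The ≥50% responder endpoint raises a different question. A rate from one or two weeks is a noisy basis for a yes/no classification, and no imputation for dropout reaches that test.

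**Working it through.** **Inputs.** Planned T+M is 14 × 7 = 98 days (Section 4). The mITT minimum is 7 diary days (Section 6.3). Dropout before Maintenance is 20% of 79 per arm (Section 4.2). The SAP gives no baseline drop-seizure rate, so r = 4 to 80 per 28 days is an assumption.

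**The plan's own figure.** For 30 points, SD 50, two-sided 0.05 and 90% power, the t-test needs 60 per group. Dividing by the Wilcoxon efficiency gives 60/0.955 = 62.8, so 63. Then 63/(1 − 0.20) = 78.75, so 79, and 3 × 79 = 237. The totals reproduce. (Section 4.2 speaks of 14 additional subjects, but 79 − 63 = 16.) Leavers per arm: 0.20 × 79 = 15.8, about 16.

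**1. Chance success with no change in seizure rate.** With mean λ = r × d/28 over d days, P(0) = e^−λ and P(0 or 1) = (1 + λ)e^−λ. For r = 8 and d = 7, λ = 2 and P(0 or 1) = 3e^−2 = 0.41.

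| Rate per 28 days | λ at 7 d | P(0), 7 d | P(0 or 1), 7 d | P(0 or 1), 14 d | P(0 or 1), 98 d |
|---|---|---|---|---|---|
| 4 | 1 | 0.37 | 0.74 | 0.41 | <0.001 |
| 8 | 2 | 0.14 | 0.41 | 0.09 | <0.001 |
| 12 | 3 | 0.05 | 0.20 | 0.02 | <0.001 |
| 20 | 5 | 0.007 | 0.04 | <0.001 | <0.001 |
| 40 | 10 | <0.001 | <0.001 | <0.001 | <0.001 |

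P(0) is the chance of a 100% reduction; P(0 or 1) is the chance of near seizure-freedom.

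**2. Clustered seizures.** With overdispersed daily counts (negative binomial, shape 0.3 per day, an assumption), the 7-day P(0 or 1) is 0.50 at rate 8, 0.19 at 20, 0.07 at 40 and 0.02 at 80.

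**3. Subjects per arm, upper bound.** Suppose all 16 leavers are in mITT with the same diary length. At rate 8 the expected number of chance near-seizure-free subjects is 16 × 0.092 = 1.5 if all have 14 days and 16 × 0.406 = 6.5 if all have 7 days. That is 1.5/79 = 2% to 6.5/79 = 8% of the arm. At rate 20 with 7 days it is 16 × 0.040 = 0.6.

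**4. The ≥50% responder endpoint.** This was simulated with unchanged rate, a Poisson 28-day baseline and DSF as in Section 8.2.1. The probability of apparent response is:

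| Rate per 28 days | 7 d | 14 d | 98 d |
|---|---|---|---|
| 8 | 0.29 | 0.19 | 0.03 |
| 20 | 0.14 | 0.07 | 0.001 |
| 40 | 0.06 | 0.01 | ~0 |
| 80 | 0.01 | 0.001 | ~0 |

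With the overdispersed counts, 7 against 98 days gives 0.38 against 0.09 at rate 8, and 0.28 against 0.03 at rate 80. The error also runs the other way. For a true 60% reduction at rate 20 (baseline fixed), response is recorded with probability 0.68 at 7 days and 0.92 at 98 days.

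**5. What S1 would do.** S1 weights the observed rate by d/98 and the baseline rate by (98 − d)/98. A subject with no seizures to day 7 then scores −100 × 7/98 = −7.1%; without S1 the score is −100%. To reach −50% needs d/98 ≥ 0.5, that is, 49 seizure-free days.

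**The case against.** The strongest reply is that this touches little that is confirmatory. Near seizure-freedom and 100% reduction are in no step of the hierarchy, and near seizure-freedom is missing even from the endpoint list in Section 5.3, although Section 3.3 names it as an objective. Section 8.2.3 rests efficacy on the primary mITT analysis, which S1 and S2 do test. All of that stands. A reader might infer that the rule inflates the type I error of the hierarchy; the SAP does not support that.

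A reader might also infer that the ≥50% responder tests share the flaw. They do not. The endpoint is a rate per 28 days and does not get easier because a count had less time to accrue. Short windows create false responders and lose true ones. The PP repeat also removes the one- and two-week leavers from a supporting analysis of steps 2 and 5. It is only a partial check, because it drops those subjects instead of scoring them and excludes others for unrelated reasons.

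A third inference would be that the ZX008 arms gain. Nothing in the SAP shows this. It needs unequal early withdrawal, for which the SAP gives no figure, and the data of early leavers in the 0.8 mg/kg/day arm come largely from titration.

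Finally, the size depends on rates that the SAP does not state. At 40 or more per 28 days with unclustered seizures, chance near seizure-freedom is negligible. That limits the size but does not supply the missing rule. The post-hoc addendum also applies near seizure-freedom to individual seizure types, whose rates cannot exceed the total, and Section 8.2.1 imputes counts for seizure clusters. Low or clustered rates are therefore plausible.

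**Conclusion.** The point holds in a limited form. Applied as written, Section 8.2.4 scores some early leavers with an unchanged seizure rate as near seizure-free, and 100% reduction does so to a lesser degree. At an assumed 8 per 28 days, the chance for a one-week leaver is 0.41, against practically nil over 98 days. On the plan's dropout allowance this is at most about 1.5 to 6.5 subjects per arm of 79. It falls to 0.6 at 20 per 28 days and to practically nil at 40 or more, unless seizures cluster. The arms are distorted against each other only if early dropout differs.

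The ≥50% responder tests have a separate and smaller problem: short-window noise in both directions, no dropout imputation, and the PP repeat as the only relevant check. The figures rest on an assumed rate, Poisson or stated overdispersed counts, and leavers who all reach mITT.

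**What to change.** In Section 8.2.4, and wherever the same categories recur (Sections 8.4.1 and 8.4.2, and the addendum), state that subjects who leave before the planned end of T+M count as not achieving 100% reduction or near seizure-freedom. Say explicitly how to score subjects who passed Visit 8 and moved into Part 2, because Section 7.1 calls them completers. A minimum-diary rule would also close the gap, but less completely.

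For steps 2 and 5, add the ≥50% responder analysis on S1-imputed DSF as a stated sensitivity analysis. The imputation is already defined in Section 8.2.3.

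The cost is SAP wording and one rerun of the responder tables. The percentages will be slightly less favourable, and a subject who leaves late while seizure-free will be scored as a failure.
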